Rare Disease Clinical Research Network

Brain Vascular Malformation Consortium

Study Title: **Sirolimus for Nosebleeds in HHT: A Phase II pilot study**

Protocol Number: 200421448

Principal Investigator: **[name] MD MSc FRCPC**

Assistant Professor, University of Toronto
Division of Respiriology, Director of the Toronto HHT Center
St. Michael's Hospital
[name]
[contact]
[contact]

Co- Investigator: **[name] MHSc MD FRCPC**

Assistant Professor, University of Toronto
St. Michael's Hospital, Respiratory and Sleep Medicine
Division of Respiriology
St. Michael's Hospital
[name]
[contact]

Clinical protocol: This protocol is for research purposes only

Phase: II

Drug: Sirolimus (1, 2 or 5mg tablets)

Effective date: Dec 12, 2023

Funded by: National Institutes of Health (NIH)

Synopsis:

This pilot study is to determine the safety and efficacy of oral sirolimus (blood trough level 6-10ng/ml) in patients with HHT that are experiencing moderate or severe epistaxis. The effect of oral sirolimus on epistaxis will be compared to baseline using the Patient-Reported Outcome of cumulative weekly nose Bleeding Duration (PRO-CB). The PRO-CB association with biomarker variability over the duration of the study will be investigated. In the pilot study subjects will be treated with 2mg of sirolimus once daily to obtain a trough level of 6-10ng/ml for 3 months.

Principal Investigator:

[name] MD MSc FRCPC

Assistant Professor, University of Toronto

Division of Respiriology, Director of the Toronto HHT Center

St. Michael's Hospital

[name]

[contact]

Number of study sites: ONE

Study site: St. Michael's Hospital, [name]

Collaborator: (study procedure)

[name], St. Michael's Hospital, Toronto, Ontario, Canada

Collaborators: (sample and data analysis)

[name], Duke University Medical Center, NC USA

[name], University of California, San Francisco

Consortium's Data Management and Coordinating Center (DMCC) at Cincinnati

Children's Hospital Medical Center

Statement of Compliance

The clinical trial will be conducted in compliance with Good Clinical Practice (GCP), the applicable regulatory requirements and according to protocol

All individuals responsible for the design and conduct of this trial have completed Human Subjects Protection Training.

1.0 Introduction and Background

The most common symptom of the hereditary hemorrhagic telangiectasia (HHT) disease is epistaxis (1). HHT is characterized by vascular (blood vessel) malformations, of the skin and mucus membranes of the nose (telangiectasia), gastrointestinal track, brain, lung and liver (1).

HHT is an autosomal dominant disease which is found in approximately 1 in 5000 individuals (1). Epistaxis affects 90% of adults with HHT, negatively affects quality of life (2, 3) and often causes anemia. Recent topical therapeutics trials have been negative (3) and surgical therapies are invasive and offer only temporary benefit at best. Currently there are no highly-effective or approved systemic therapies for HHT-related epistaxis, but this is an area of active research and development. There is considerable in developing and identifying therapies that target the abnormal biology and mechanisms in HHT, including antiangiogenic therapies, such as bevacizumab (1). Bevacizumab, however, is associated with significant toxicity, costly and administered intravenously.

Over the past few years, there has been considerable new evidence of the pathways involved in HHT disease and related potential therapeutic targets, including the mTOR pathway. Evidence suggests that HHT pathogenesis strongly relies on overactivated PI3K-Akt-mTOR and VEGFR2 pathways in endothelial cells. Ruiz et al (4) recently reported that the mTOR inhibitor, sirolimus, and the receptor tyrosine-kinase inhibitor, nintedanib, synergistically fully blocked, and also reversed, retinal AVMs, in the BMP9/10- immunoblocked neonatal mouse model of HHT. Subsequent unpublished preliminary data demonstrated that sirolimus was more effective than nintedanib at blocking anemia and bleeding in inducible ALK1 knockout HHT mice, and similarly effective to combined sirolimus-nintedanib. As such, sirolimus may provide therapeutic benefit for HHT patients (5). Human studies have shown “low-dose” sirolimus to be low risk and effective as a treatment for other vascular anomalies (6)(7).

There is an urgent need for effective therapies for HHT and the chronic bleeding associated with the disease. Preliminary cellular and animal model data have identified sirolimus as a potential new pathway-based therapy in HHT. In addition, sirolimus is an interesting agent, as it is given orally and is available for repurposing. Data from other vascular malformations syndromes suggest that it can be effective in a “low-dose” range, reducing risk of toxicity, but there is only one published case report of sirolimus use in an HHT patient. This phase II pilot study will provide safety data as the primary outcome, and secondarily, efficacy data, outcome measure data and biological exploratory data, to support the planning of a future randomized and placebo-controlled clinical trial of sirolimus for epistaxis in HHT patients.

2.0 Rationale

Sirolimus has been identified as a potential pathway-based therapy for HHT. Pre-clinical research has suggested that the pathogenesis of HHT is as a result of overactive mTOR and VEGFR2 pathway (4). Sirolimus has been found to work as an mTOR inhibitor to prevent the effects of overactive mTOR that results in arteriovenous malformations in a HHT (4). One clinical trial that used sirolimus to treat vascular anomalies, found that sirolimus was well

tolerated and acted as an effective and safe treatment for most study participants (6). Considerable experience using sirolimus in post-transplant patients and growing experience using sirolimus in patients with vascular anomalies exist. This pilot study will assess the safety and effectiveness of repurpose oral sirolimus, for epistaxis in patients with HHT.

3.0 **Objectives and Purpose**

There is an urgent need for effective therapies for HHT and this sirolimus pilot study will provide safety and outcome measures to guide planning of a future randomized and controlled clinical trial.

The hypothesis

We hypothesize that oral sirolimus (blood trough level 6-10ng/ml) will be a safe and effective therapy for epistaxis in HHT patients.

3.1 Purpose

Aims	Endpoint
Specific Aim 1 To determine the safety of a 6-10ng/ml dose oral sirolimus in patients with HHT, with moderate or severe epistaxis.	Clinical and laboratory adverse event (AE) measures, as per detailed Safety Monitoring:
Specific Aim 2A: To measure the effect of a 6-10ng/ml dose of oral sirolimus on epistaxis in HHT patients, compared to baseline epistaxis	Epistaxis will be measured using the Patient-Reported Outcome of cumulative weekly nose Bleeding Duration (PRO-CB), compared to baseline PRO-CB, obtained from daily epistaxis diary.
Specific Aim 2B: To characterize PRO-CB in HHT patients with moderate to severe epistaxis.	PRO-CB using daily diary throughout the 9 months of the study.
Specific Aim 3: To explore biomarkers variability over time, on/off therapy and association with PRO-CB.	We will collect plasma for biomarkers (specific panel will be determined with the HHT Study team which may include the following: ANG2 sICAM1 PIGF TSP2 sVEGFR2, BMP9 IL6 SDF1 sVCAM1 sVEGFR3, sCD73 sIL6R TGFβ1 VEGF, sENG OPN TGFβ2 VEGF-C, GP130, PDGF-AA, sTGFβR3, VEGF-D, HGF PDGF-BB, TIMP1, sVEGFR1 (Wetzel-Strong et al. Orphanet J Rare Dis (2021) 16:372)

4.0 **Research Plan**

Sirolimus is a potential therapy of interest in HHT, The primary outcome is the reduction of epistaxis (minutes per week), as adults with HHT are almost universally affected by epistaxis and it is known to impair quality of life (3). The study aims to investigate subjects with moderate to severe epistaxis, using sirolimus target trough 6-10 ng/ml for 3 months.

4.2 Study Participants:

The study will include a maximum of 20 enrolled participants with a final target of 10 subjects who entirely or partially complete study drug intervention. Participants will be recruited from the Toronto HHT Center, at St. Michael's Hospital, and through the Rare Diseases Network website (<https://www1.rarediseasesnetwork.org/cms/bvmc/Get-Involved/Studies>).

The primary outcome for the trials will be the reduction of epistaxis severity (minutes of bleeding per week).

4.3 Inclusion and Exclusion Criteria:

4.3.1 Inclusion criteria:

- a) Age \geq 18 years
- b) Clinical HHT diagnosis (8) or genetic diagnosis of HHT
- c) Epistaxis at least 15 min per week.
- d) COVID-19 Vaccine (2 doses)
- e) Ability to give written informed consent, including compliance with the requirements of the study.

4.3.2 Exclusion criteria:

- a) Allergy/intolerance to the study drug or related agents
- b) Unstable medical illness
- c) Acute infection
- d) Creatinine > ULN (upper limit of normal)
- e) Liver transaminases (AST or ALT) \geq 2x ULN
- f) Women participant who are pregnant or breastfeeding or plan to become pregnant during the duration of the study
- g) Women of childbearing potential not on effective contraception.
- h) Male participants of reproductive potential whose female partners are of childbearing potential and are not planning to use highly effective contraceptive method
- i) Immunocompromised
- j) History of malignancy
- k) Known untreated dyslipidemia (20% above the ULN of total cholesterol and triglycerides)
- l) Specific contra-indications for study drug (detailed in the product monograph)

5.0 Study Design

This pilot study (final n=10) of oral sirolimus (starting dose of 2mg once daily, adjusted to maintain drug blood levels of 6-10 ng/ml, 3-month course) in HHT subjects with moderate-severe recurrent epistaxis. The subjects recruited will have zero or greater than two telangiectases of \geq 2 mm diameter available for excisional biopsy

5.1 Schedule of Events

- i. Screening visit: Confirm eligibility
- ii. Baseline: All subjects will undergo a 3 month baseline period following the screening visit
- iii. Study drug arm: Subjects will be treated with a 3 month course of sirolimus at a starting dose of 2mg once daily. This dose will be adjusted as needed, to maintain drug blood levels of 6-10 ng/ml.
- iv. Follow up: All subjects will undergo a 3 months follow-up period.

5.2 Study Design Discussion

All participants will receive 3-month course of study drug

The collaborating doctor ([name]) will advise on dose adjustment to maintain a drug blood level of 6-10 ng/ml.

A medical history and physical examination will be performed at all clinic visits.

5.2.1 Specific study drug dosing:

Sirolimus starting dose of 2 mg once daily, orally adjusted as need to maintain drug blood levels of 6-10 ng/ ml

The first dose will be given at the week 12 visit and participants will be observed for 30 min

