5.3 Study Timelines

The study is expected to take place over a period of 9 months; all subjects will have a screening visit for eligibility review and informed consent. Participants will start with a baseline period of 3 months, treatment period of 3 months (study drug), and a follow-up period of 3 months. Tissue biopsy will occur prior to the start of study drug and at the end of the study drug period

5.3.1 Baseline period:

There will be a 3-month baseline period for accurate measurement of primary outcomes; epistaxis severity in minutes of bleeding per week. Participants will be asked to keep a daily diary of all epistaxis events, recording duration and intensity for each, for the three months baseline period and the duration of the study.

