5.3.3 Follow-up period

There will be a follow-up period of 3 months post the investigational product period, during which safety and outcome data will be collected.

5.4 Table of Study visit Summary:

*Visit Summary	***Weeks (time Point)	****Blood work (safety) + Biomarkers	Daily Diary (DD)+ Epistaxis severity score (ESS)	Safety and Adverse event Monitoring, Medical history	Tissue biopsy	Pill count
Screening Clinic visit/ ICF	0	Safety	DD+ESS	X	X	
Phone Visit/ baseline period	1,2,4,6,8,1 0		DD	X		
Investigational product assignment/ clinic visit/(day 0)	12	Safety + biomarker	DD+ESS	X		X
**Dose adjustment (as needed)	13	Safety		X		
Phone visit	14,16		DD	X		
Clinic visit (6 weeks investigational product)	18	Safety + biomarker	DD+ESS	X		X
Phone visit	20, 22		DD	X		
Clinic Visit (12 weeks) End of investigational product	24	Safety + biomarker	DD+ESS	X	X	X
Start of Follow-up Period, Phone visit	26, 28, 30, 32, 34		DD	X		
Final Epistaxis daily diary documentation	36	Safety + biomarker	DD+ESS	X		

* Medical History and Physical Examination at all clinical visits..

** a blood sample will be collected for sirolimus blood level, for dose adjustment

*** +/- 7 days, unscheduled clinic visit or safety blood work – will occur if required to assess safety and for women of childbearing potential on effective contraceptive – will occur if required to assess safety and for women of childbearing potential on effective contraceptive.

****safety blood work will include: Electrolytes (Sodium, Potassium, Chloride, total CO₂), Hematology (total blood count-CBC), Renal Function test (urea, creatinine), Liver function (AST, ALT, total Bilirubin), ferritin level, Pregnancy test (BHCG level) and sirolimus blood level, blood glucose level, lipid assessment (total Cholesterol, Triglycerides)

*****Biopsy samples will be collected if the subject have two skin telangiectases of >2mm diameter available for excisional biopsy, prior to the start of study drug and at the end of treatment period.

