6.1 Study drug

Six weeks of study drugs will be dispensed at each study drugs visit (and an additional amount for 7 days of study visit window). Investigational product will be stored according the manufacturer's recommendations. The Pharmacy staff will keep a study temperature log for the study drugs. A drug accountability log will be kept by the Pharmacy staff [dispensing information (date and pill number) and drug return information will be recorded].

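### The first sirolimus dose is given at the visit where creatinine, AST/ALT and hCG are next drawn, with no requirement to read those results first, so the last results sure to be known are about 12 weeks old

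*Protocol*

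**What the plan says.** Eligibility is placed at the start. Protocol Section 5.1 lists "Screening visit: Confirm eligibility", and Section 5.3 says that "all subjects will have a screening visit for eligibility review and informed consent". A three-month baseline period follows.

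Among the exclusions in Section 4.3.2 are d) "Creatinine > ULN (upper limit of normal)", e) AST or ALT at or above twice the ULN, and f) "Women participant who are pregnant or breastfeeding or plan to become pregnant during the duration of the study".

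In Table 5.4 the baseline contacts at weeks 1, 2, 4, 6, 8 and 10 are phone visits with an empty blood-work cell. The week-12 row, labelled "Investigational product assignment/ clinic visit/(day 0)", carries safety and biomarker blood work. The table's footnote defines the safety panel to include creatinine, AST, ALT and hCG.

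For the same visit, Section 5.2.1 says: "The first dose will be given at the week 12 visit and participants will be observed for 30 min". Section 6.1 adds: "Six weeks of study drugs will be dispensed at each study drugs visit", with a further seven days' supply to cover the visit window.

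**The concern.** Exclusions d, e and f exist to keep certain participants off sirolimus. The plan applies them about three months before anyone receives the drug. It draws a fresh sample at the right visit but does not say that the result must be seen before the tablets are given. Creatinine and transaminases are laboratory values, so phone contact, history and examination cannot recheck them. Pregnancy can be asked about by phone, but no test is specified there.

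At stake is a participant who was eligible at week 0, meets one of these exclusions by week 12, takes the first dose and goes home with drug before the result is known. Safety is Specific Aim 1 and the primary outcome in Section 7.1. With a target of about ten treated participants, even one dosed outside the entry limits would make the safety data harder to read.

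**Working it through.** No sample-size or power calculation bears on this point. The check is date arithmetic on Table 5.4, plus a search for any rule that holds the first dose.

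**Age of the last guaranteed result**
- Screening safety blood: week 0. First dose: week 12 (Table 5.4, Section 5.2.1).
- Interval: (12 − 0) × 7 = 84 days, matching the three-month baseline in Section 5.1.
- With the ±7-day window on the week-12 visit: 84 − 7 = 77 to 84 + 7 = 91 days.

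**Scheduled blood draws in between**
- Baseline contacts: weeks 1, 2, 4, 6, 8, 10 = 6 phone visits, 0 with blood work.
- Sections 10.0 and 10.1 speak of clinic visits, and of hCG at them, every six weeks. Table 5.4 makes week 6 a phone visit without blood work, and Section 7.1 describes baseline monitoring as by phone only. A week-6 laboratory result cannot be relied on.

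**Drug in hand at day 0**
- 6 × 7 + 7 = 49 days' supply.

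**Exposure before the week-12 result is known**
- Turnaround is not stated. Assumed range: 1 to 3 days.
- Once-daily dosing at the 2 mg starting dose: 1 × 2 = 2 mg to 3 × 2 = 6 mg.
- Same-day result read before dosing: 0 mg.

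**Rules that might hold the first dose**

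| Provision | What it does | Holds the first dose? |
|---|---|---|
| 9.2, blood at each clinic visit | Ensures the sample is drawn | No; says nothing about reading it first |
| 10.1, hCG above 24 IU/L | Requires immediate discontinuation | Only once a result exists |
| 13.0, withdrawal | Lets the investigator withdraw at any time, including for ineligibility found later | No; permissive |
| Table 5.4 footnote ("7 days, unscheduled clinic visit or safety blood work") | Extra bloods if required for safety | No; a silent laboratory change would not prompt them |
| 4.3.2 g and h, phone pregnancy monitoring | Lower the chance of pregnancy | No; and they do not bear on creatinine or AST/ALT |
| Table 5.4, week-13 safety draw | Sampling one week into treatment | No; comes after dosing |

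No provision makes the first dose or the dispensing conditional on the week-12 panel.

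**The case against.** The strongest reply is that this argues from silence. The protocol does not say that dosing comes before the results. Drawing blood, reading it and then dosing fits the text equally well, and a careful site may do just that. The protocol also refers to a monitoring plan and a product monograph that are not shown here. This stands as far as it goes: the plan permits the risk rather than directing it. But a site that doses before the results are back is fully compliant, and conditions for dosing belong in the protocol.

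A second reply is that the consequence is small. Neither the 84 days nor the 49 days is time spent on drug without a result. The week-12 sample is drawn regardless, its result can be acted on, and another safety draw follows at week 13. That is correct, and it limits the exposure to the turnaround time.

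A third is that creatinine and transaminase limits are entry criteria, that the protocol sets no on-treatment threshold for either, and that a marginal rise at week 12 need not bar treatment. There is something in this, since what to do about a small rise is a clinical judgement. But that judgement should be made before the first dose, with the result in view.

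Finally, pregnancy is the best-covered risk, through required contraception, phone monitoring and mandatory discontinuation on a positive result. This lowers the risk but does not ensure that a test result is seen before the first dose.

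**Conclusion.** The concern holds. As written, the protocol guarantees only laboratory results 84 days old (77 to 91) at first dose and permits dosing and dispensing before the week-12 panel is read. The likely exposure of an affected participant is brief: 1 to 3 doses, 2 to 6 mg, if results take 1 to 3 days, and none with a same-day result seen first. Turnaround is assumed. The chance that a participant crosses a criterion during baseline is not given and is not estimated. The change should be made because the exclusions are the protocol's own, safety is the first aim, and the sample needed is already scheduled. The small size of the exposure keeps this short of a critical flaw.

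**What to change.** In Section 5.2.1 and Table 5.4, require that the week-12 safety panel be drawn within the seven days before the first dose, or that a same-day result be obtained. Require exclusions 4.3.2 d, e and f to be reconfirmed on those results before drug is dispensed. The biomarker sample can stay on day 0, and the panel still serves as the pre-treatment laboratory baseline.

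The cost is small. No new test is needed; some participants would make one extra trip for the blood draw, avoided where a same-day result is available. A participant found ineligible at week 12 may need replacing. Section 4.2 allows up to 20 enrolled for a final target of 10, so there are 20 − 10 = 10 places to absorb this.

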5.3 Study Timelines

The study is expected to take place over a period of 9 months; all subjects will have a screening visit for eligibility review and informed consent. Participants will start with a baseline period of 3 months, treatment period of 3 months (study drug), and a follow-up period of 3 months. Tissue biopsy will occur prior to the start of study drug and at the end of the study drug period

5.3.1 Baseline period:

There will be a 3-month baseline period for accurate measurement of primary outcomes; epistaxis severity in minutes of bleeding per week. Participants will be asked to keep a daily diary of all epistaxis events, recording duration and intensity for each, for the three months baseline period and the duration of the study.

5.3.2 Treatment period

There will be a 3- month treatment period of sirolimus.

5.3.3 Follow-up period

There will be a follow-up period of 3 months post the investigational product period, during which safety and outcome data will be collected.

5.4 Table of Study visit Summary:

*Visit Summary	***Weeks (time Point)	****Blood work (safety) + Biomarkers	Daily Diary (DD)+ Epistaxis severity score (ESS)	Safety and Adverse event Monitoring, Medical history	Tissue biopsy	Pill count
Screening Clinic visit/ ICF	0	Safety	DD+ESS	X	X	
Phone Visit/ baseline period	1,2,4,6,8,1 0		DD	X		
Investigational product assignment/ clinic visit/(day 0)	12	Safety + biomarker	DD+ESS	X		X
**Dose adjustment (as needed)	13	Safety		X		
Phone visit	14,16		DD	X		
Clinic visit (6 weeks investigational product)	18	Safety + biomarker	DD+ESS	X		X
Phone visit	20, 22		DD	X		
Clinic Visit (12 weeks) End of investigational product	24	Safety + biomarker	DD+ESS	X	X	X
Start of Follow-up Period, Phone visit	26, 28, 30, 32, 34		DD	X		
Final Epistaxis daily diary documentation	36	Safety + biomarker	DD+ESS	X		

* Medical History and Physical Examination at all clinical visits..

** a blood sample will be collected for sirolimus blood level, for dose adjustment

*** +/- 7 days, unscheduled clinic visit or safety blood work – will occur if required to assess safety and for women of childbearing potential on effective contraceptive – will occur if required to assess safety and for women of childbearing potential on effective contraceptive.

****safety blood work will include: Electrolytes (Sodium, Potassium, Chloride, total CO₂), Hematology (total blood count-CBC), Renal Function test (urea, creatinine), Liver function (AST, ALT, total Bilirubin), ferritin level, Pregnancy test (BHCG level) and sirolimus blood level, blood glucose level, lipid assessment (total Cholesterol, Triglycerides)

*****Biopsy samples will be collected if the subject have two skin telangiectases of >2mm diameter available for excisional biopsy, prior to the start of study drug and at the end of treatment period.

